#### Missing data

Subjects with missing data in the exposure (e.g. missing date at vaccination) or health outcome variables (e.g. missing data at symptom onset) will be excluded.

For each covariate, the amount and possible reason for missing data will be described. For covariates for which the amount of missing data at the study site level is not substantial (<15%), we will introduce an additional missingness category.

For covariates for which the amount of missing data is substantial (>=15%), multiple imputation methods will be applied assuming that the missingness does not depend on unobserved variables. A sensitivity analysis will be carried out comparing the IVE estimates based on the multiple imputation approach with the IVE estimates based on a complete case analysis (e.g. omitting records with missing covariate information from the analysis).

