## **Exposure (vaccination)**

#### Exposure of interest

The exposure of interest is vaccination with any influenza vaccine (seasonal or pandemic) in the season under investigation. It is crucial to know precisely the date of vaccine administration, the type/brand of the vaccine and the date of symptoms' onset as well as the date of specimen collection.

The vaccine type specific VE may be assessed e.g.

- by strategy used for influenza antigen preparation (live attenuated, inactivated, subunit, split virion),
- by number of vaccine virus strains contained in the different vaccines available (trivalent, tetravalent)
- by adjuvant (adjuvanted, non-adjuvanted)
- by vaccine dose (one dose, two doses; 0,25 ml, 0,5 ml)
- by manufacturing process (egg-based, cell-based)

The vaccine types selected to primary and potential sensitivity analyses will be specified in the generic study site level SAP, which will be updated annually, if needed.

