#### Definition of vaccination status

An individual aged  $\geq$ 9 years, or a child aged <9 who has been fully vaccinated (at least two injectable doses or one LAIV dose) during the previous influenza season will be considered as

- vaccinated with the influenza vaccine of interest if he/she has a record of influenza vaccine administration >14 days before ILI/SARI symptom onset (see section Vaccination status ascertainment)
- partially vaccinated if he/she has a record of influenza vaccine administration ≤14 days

before ILI/SARI symptom onset

- **unvaccinated** if he/she has no influenza vaccine record for the current season
- **potentially vaccinated** if the positive vaccination status is based on recall alone and cannot be confirmed by registers, or is otherwise ambiguous.

A child aged < 9 years who has not been fully vaccinated (see above) during the previous influenza season will be considered as

- **vaccinated** with the influenza vaccine of interest if >14 days have elapsed since the second record of injectable vaccination or the first record of LAIV vaccination during the current season (see section *Vaccination status ascertainment*)
- partially vaccinated
  - during the first 14 days after the second record of injectable vaccination or the first record of LAIV vaccination during the current season
  - after the first record of injectable vaccination until >14 days have elapsed since the second record of vaccination during the current season
- **unvaccinated** until the first vaccination record during the season
- **potentially vaccinated** if the positive vaccination status is based on recall alone and cannot be confirmed by registers, or is otherwise ambiguous.

The *partially* and *potentially* vaccinated groups will be excluded from primary analysis; their significance will be assessed in sensitivity analyses.

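### Vaccinees with a missing vaccination date are excluded, and partial dates cannot be recorded, although a bound on the date would often settle the 14-day exposure rule

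*Combined protocol and SAP*

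**What the plan says.** Under Statistical analysis, the Missing data section excludes two groups: "Subjects with missing data in the exposure (e.g. missing date at vaccination" is the first, and the sentence ends with the outcome variables, "e.g. missing data at symptom onset) will be excluded". Describing the amount and reasons of missingness, the missing-category method, multiple imputation and the complete-case comparison are all prescribed for covariates.

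The Definition of vaccination status section sets a threshold. For people aged 9 or over, and children under 9 fully vaccinated the season before, it asks for "a record of influenza vaccine administration >14 days before ILI/SARI symptom onset". For other children given injectable vaccine, status holds "if >14 days have elapsed since the second record of injectable vaccination"; for LAIV the first dose counts.

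The same section has a potentially vaccinated group, for positive status known from recall alone that "cannot be confirmed by registers, or is otherwise ambiguous". That group and the partially vaccinated are left out of the primary analysis, but "their significance will be assessed in sensitivity analyses".

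In Annex 1, seasvaccdate is obligatory in dd/mm/yyyy form. Neither it nor the child dose-date fields has a code for a partial date or a bound.

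**The concern.** To classify a vaccinee, the primary analysis needs only to know on which side of day 14 the qualifying dose fell. The codebook's own example onset is 29/12/2017. For an adult with that onset, a record saying only November 2017 puts vaccination at least 29 days earlier (30 November to 29 December), so status is certain without the day. The accepted sources include GP and pharmacist interviews and insurance delivery or reimbursement data, which may yield a month or a delivery date rather than a day of administration. The plan has no rule for these.

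Only a vaccinee can lack a vaccination date, so the date part of the exclusion thins the vaccinated cells and leaves the unvaccinated ones intact. This costs precision. It also makes the odds ratio depend on whether dates are found equally often for cases and controls. Nothing in the plan requires undated vaccinees to be counted by case status, so an imbalance could go unseen.

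**Working it through.** **Inputs.** From the protocol's Sample size considerations and Annex 3 (Precision): 500 cases, 1:1 ratio, true VE 50% (OR 0.5), two-sided 95% CI, and coverage γ taken over all subjects, so the vaccinated number Nγ of N = 1000. Undated shares of 10, 20 and 30% and the retrieval rates below are assumptions; the documents give none.

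**Formula.** Annex 3, equation (3): lower limit = 1 − exp[log(OR) + 1.96 × SE], with SE = √(1/a + 1/b + 1/c + 1/d). Here a and b are vaccinated cases and controls; c and d are unvaccinated cases and controls.

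**The plan's figure.** Solving for the cells gives:
- 20% coverage: 72.8 / 127.2 / 427.2 / 372.8. SE = √(0.01374 + 0.00786 + 0.00234 + 0.00268) = 0.1631; limit = 1 − 0.5 × exp(1.96 × 0.1631) = 31.2%.
- 50% coverage: 207.1 / 292.9 / 292.9 / 207.1; SE 0.1284; limit 35.7%.
- 70% coverage: 314.1 / 385.9 / 185.9 / 114.1; SE 0.1411; limit 34.1%.

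The plan's statement of a limit above 30% is reproduced.

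**Equal loss in cases and controls.** With undated share m, a and b become a(1 − m) and b(1 − m); VE stays at 50%. Example at 20% coverage, m = 0.20: SE = √(0.02160/0.8 + 0.00502) = 0.1789; limit = 1 − 0.5 × exp(0.3507) = 29.0%.

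| Coverage | m = 0 | 10% | 20% | 30% | SE increase |
|---|---|---|---|---|---|
| 20% | 31.2% | 30.2% | 29.0% | 27.5% | 4 / 10 / 16% |
| 50% | 35.7% | 35.2% | 34.7% | 34.0% | 3 / 6 / 10% |
| 70% | 34.1% | 33.8% | 33.4% | 33.0% | 2 / 4 / 6% |

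For a brand with 40% of vaccinations at 50% coverage (a and b multiplied by 0.4, c and d kept), the limit goes from 30.2% to 29.3, 28.2 and 26.9%, still above the 25% the plan states for such brands.

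**Unequal loss.** With dated shares f₁ in cases and f₀ in controls, observed OR = 0.5 × f₁/f₀.
- 90% and 80%: 0.5 × 1.125 = 0.5625; VE 43.8%.
- 95% and 90%: 0.5 × 1.056 = 0.528; VE 47.2%.
- 80% and 90%: 0.5 × 0.889 = 0.444; VE 55.6%.

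**With date bounds.** If bounds settle 80% of undated vaccinees and 20% are undated, 0.2 × 0.2 = 4% stay unresolved; the limits are 30.8% (20% coverage) and 35.5% (50% coverage). In the 90%/80% example, settling 80% gives retained shares of 0.98 and 0.96, so VE = 1 − 0.5 × 0.98/0.96 = 49.0%. The share that bounds would settle is again an assumption.

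**The case against.** The best defence is that requiring a date is deliberate. Exposure of interest says "It is crucial to know precisely the date of vaccine administration", and the secondary objective on time since vaccination cannot be met without it. That stands for the time-since-vaccination analyses. It does not justify dropping subjects from estimates that need only the threshold.

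The plan may also already have a place for these subjects: a confirmed but undated vaccination could count as ambiguous and so as potentially vaccinated, with a sensitivity analysis to follow. The general Sensitivity analyses section also permits other exposure definitions. This stands in part. The plan does not say which section governs, so sites could code the same subject differently, and both routes remove the subject from the primary analysis.

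Several stronger readings are tempting but unsupported:
- That the text excludes everyone without an exact day. It says missing; the exact-day requirement comes from the codebook format.
- That the whole rule removes only exposed subjects. This is true of the date example, but unknown vaccination status is missing exposure too, and those subjects may be unvaccinated.
- That the loss always falls on the scarcest cell. Both vaccinated cells are thinned; for overall VE, vaccinated cases tie with unvaccinated controls at 50% coverage, and unvaccinated controls are smallest at 70%.
- That VE is biased. The documents give no retrieval rates, and the questionnaire is completed at swabbing, which makes differential retrieval less likely. Permitted rapid tests and later data-cleaning queries keep it possible.
- That unknown brand removes a subject from overall VE. Annex 1 holds any vaccination and brand as separate variables, so this merits only a clarifying sentence.

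Nor do the documents show how many dates a bound would settle. The study period can be extended to cover the vaccination campaign, so some doses will lie close to onset.

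**Conclusion.** The point holds as a better analysis choice available at little cost. The plan discards verified vaccinees whose status a date bound would settle, and leaves the Missing data and Definition of vaccination status sections unreconciled for them. The precision loss is modest: about one to four points on the lower limit at 20% coverage and half a point to under two at 50%, for assumed undated shares of 10 to 30%. At 20% coverage, the edge of the range for which the plan states a limit above 30%, that limit survives 10% undated but not 20%. Bias is conditional on unequal date retrieval. It would lower VE if dates were found more often for cases and raise it if more often for controls.

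**What to change.** - Let seasvaccdate and the child dose-date fields take month and year, or a latest possible date.
- Apply the existing status definitions to the earliest and latest possible date of the qualifying dose. For children under 9 not fully vaccinated the season before, that is the second injectable or first LAIV dose; the existing rule for a single injectable dose is unchanged.
- Class as vaccinated if the latest possible date is more than 14 days before onset. Class as partially vaccinated on the date only if the whole possible interval lies within the 14 days up to onset. Otherwise treat as undetermined: out of the primary analysis and into the sensitivity analysis of potentially vaccinated subjects.
- Amend the Missing data section to refer to this rule, so that one section governs.
- Require exact dates only for time-since-vaccination analyses, and exclude unknown brand only from brand- and type-specific models.
- Tabulate undated vaccinees by case status, and add an exact-date-only sensitivity analysis.

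The cost is a short change to the Missing data text, one extra codebook format, and slight exposure misclassification near day 14.

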# **Methods**

#### Study design

> A multicentre study using data from several study sites

In each participating study site, an observational case-control study using the test-negative design

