## Sample size considerations

This section gives sample size considerations and formulates recommendations. These recommendations are meant to support the design of the case-control studies on IVE. Obtaining a minimum sample size is not a requirement for study participation. Details on the sample size calculations based on the minimal detectable VE as well as precision are given in Annex 3.

DRIVE recommends case-control studies based on 500 cases or more. However, studies with smaller sample sizes might still contribute to the power of the pooled analyses, provided that the study site is able to optimally harmonise its protocol with the other study sites to minimize the

between-study heterogeneity. In case VE estimates with unacceptable large CIs are obtained, it might be considered to not report these estimates.

Figure 1 presents the precision of the overall VE for number of cases varying from 200 to 4000 subjects, when assuming a true VE of 50%, a 'cases to controls' ratio of 1:1 and a total vaccination coverage of 5%, 20%, 50% and 70%. The number of cases per control is likely to vary (by definition of test-negative design). The calculations are based on an anticipated true VE of 50% as this is a conservative choice, requiring larger sample sizes compared to assuming lower/higher VE values. A case-control study based on 500 cases and a 1:1 'cases to controls' ratio will result in 95% CIs of the overall VE with a lower limit larger than 30% given a true VE of 50%, for coverages of >20%.

**Figure 1.** Precision of the overall VE expressed as the lower limit of the 95% CI, assuming a true VE of 50%, a 'cases to controls' ratio of 1:1 and a total vaccination coverage of 5%, 20%, 50% and 70%.

Figure 2 presents the precision of the brand-specific VE for number of cases varying from 200 to 4000 for the same parameter settings as above and additionally assuming the brand of interest accounts for 10%, 20%, 40%, 60%, 80% and 90% of the total vaccination coverage. A case-control study based on 500 cases and a 1:1 'cases to controls' ratio will result in 95% CIs of the brand-specific VE with a lower limit larger than 25% given a true VE of 50%, for brands covering 40% to 90% of the influenza vaccines when the overall vaccination coverage is 50% or more.

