#### Measure of effect

The crude (or unadjusted) brand-specific IVE will be estimated as

$$VE = (1 - OR) \times 100\%$$
,

where *OR* denotes the odds ratio, comparing the odds of vaccination among influenza-positive study participants by the odds of vaccination among influenza-negative study participants. The 95% confidence intervals will be obtained as well.

Confounder-adjusted brand-specific IVE estimates will be obtained from multivariable logistic regression models, regressing the health outcomes of interest on exposure status, age, sex and the confounders of interest. In case of effect modifiers, an interaction term between exposure and the effect modifier will be included in the regression model or stratified regression analyses will be performed.

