#### Addressing confounding & bias

Observational influenza vaccine effectiveness studies are prone to several sources of confounding and other types of bias. Please also refer to section *Potential confounders and effect modifiers* and

DRIVE D2.2: Systematic review of the sources of confounding, bias and strategies to manage their impact in influenza vaccine effectiveness studies.

- Negative confounding refers to biases that reflect the fact that high risk groups (people more likely to develop severe complications) will be more likely to be vaccinated and therefore reduce VE. If negative confounding is present, the VE will be underestimated. Adjustment for potential negative confounding factors documented in the study (e.g. presence of chronic diseases) will minimise negative confounding.
- Positive confounding refers to biases that reflect a 'healthy vaccine effect'. People with a
  healthy lifestyle will be more likely to accept vaccination, thus leading to an increase of
  measured VE. Or, similarly, people being in a state of "extreme frailty" will not be offered
  vaccination. If positive confounding is present, VE will be overestimated.

Thus, it is important to collect information on both the frailty and the healthcare seeking behaviour adequately and to balance possible differences between the vaccinated and the unvaccinated in the study population.

As the data are collected directly form GPs it is difficult that misclassification (information bias) might occur. In any case, during the DRIVE collaboration process, the potential confounders and biases as well as strategies to reduce their impact in VE studies will be identified by a systematic literature review (DRIVE D2.2), and the protocol may be updated accordingly.

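### Adding a missingness category for confounders under 15% missing leaves some residual confounding in the adjusted VE; the planned multiple imputation should cover every incomplete confounder

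*Combined protocol and SAP*

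**What the plan says.** The Missing data section of the protocol's Statistical analysis sets the method covariate by covariate, on the percentage missing at the study site. Below the threshold, where missingness "is not substantial (<15%), we will introduce an additional missingness category". At 15% or more, "multiple imputation methods will be applied assuming that the missingness does not depend on unobserved variables". The section's one sensitivity analysis is "comparing the IVE estimates based on the multiple imputation approach with the IVE estimates based on a complete case analysis". It also asks sites to describe the amount of missingness and the possible reasons. It does not say why the method should change at 15%.

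The later Sensitivity analyses section names no missing-data analysis, and the pooled plan in Annex 4 refers back to the protocol for its own.

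Three other passages show what the covariates are for. The design at each site is "an observational case-control study using the test-negative design". Under Measure of effect, "Confounder-adjusted brand-specific IVE estimates will be obtained from multivariable logistic regression models". Under Addressing confounding & bias, "Adjustment for potential negative confounding factors documented in the study (e.g. presence of chronic diseases) will minimise negative confounding".

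**The concern.** A missingness category puts everyone with an unknown value into one stratum. Within that stratum, people with and without the confounder are mixed, so the vaccination odds ratio there is unadjusted for it. The model's single vaccination coefficient then blends an adjusted comparison with an unadjusted one. In a randomised trial this does little harm, because the covariate is balanced between arms. Here nothing balances it except the adjustment itself. The resulting bias exists even under missing completely at random (MCAR), and a larger sample does not reduce it.

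The rule reaches variables that matter. Chronic disease, number of hospitalisations and healthcare visits are in the minimum confounder set for pooling, and their Annex 1 entries allow a no-information code. The better method is already in the plan, but it is kept for the covariates with the most missing data.

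**Working it through.** **1. The plan's own precision, as a yardstick.** Annex 3, equation (3): lower limit = 1 − exp[log(OR) + 1.96 × √(1/a + 1/b + 1/c + 1/d)]. Inputs from the protocol: true VE 50% (OR 0.5), 500 cases and 500 controls, two-sided 95% interval. The cells follow from the OR and the coverage.

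| Coverage | a, b, c, d | Standard error | Lower limit | Distance from 50% |
|---|---|---|---|---|
| 20% | 72.8, 127.2, 427.2, 372.8 | 0.163 | 31.2% | 18.8 points |
| 50% | 207.1, 292.9, 292.9, 207.1 | 0.128 | 35.7% | 14.3 points |
| 70% | 314.1, 385.9, 185.9, 114.1 | 0.141 | 34.1% | 15.9 points |

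At 20% coverage, for example: 1 − 0.5 × exp(1.96 × 0.1631) = 0.312. The stated lower limit above 30% is reproduced. The yardstick is 14 to 19 points.

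**2. Bias from one incomplete confounder.** The documents give no confounder strengths or missingness rates, so these are assumptions: one binary confounder C with 40% prevalence; 20% vaccinated when C is absent; 50% test positivity in the unvaccinated without C; MCAR. The calculation is a large-sample logistic regression on the exact joint distribution of C, vaccination V and test result, so it carries no simulation noise. The fitted model is logit P(positive) = β0 + βV·V + βC·(C known and present) + βM·(C missing), with VE = 1 − exp(βV). The true VE is 50%.

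| OR of C with vaccination, influenza | Crude VE | VE, 14% missing | VE, 5% missing |
|---|---|---|---|
| 3, 1.5 | 44.0% | 49.1% | 49.7% |
| 3, 2 | 38.9% | 48.4% | 49.4% |
| 5, 3 | 21.8% | 45.9% | 48.5% |
| 10, 3 | 10.3% | 43.8% | 47.7% |
| 10, 0.5 | 64.2% | 52.9% | 51.1% |

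Full-data adjustment gives 50.0% in every row, and so does complete case under MCAR. At 14% missing the bias runs from under 1 point to about 6 points; at 5%, from 0.3 to 2.3 points. Baseline positivity matters little: for ORs 5 and 3 at 14% missing, VE is 46.7% at 10% positivity against 45.9% at 50%. Multiple imputation was not simulated. The full-data value is what a correctly specified imputation aims at when data are missing at random (MAR).

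**3. Several incomplete confounders.** Assume independent confounders, each with 40% prevalence, ORs 3 and 2, and 14% missing independently; 10% vaccinated and 30% positive when none is present. VE is then 48.5%, 47.0%, 45.5% and 44.1% for one, two, three and four covariates. The share of records with at least one missing level is 1 − 0.86³ = 36% for three covariates and 1 − 0.86⁴ = 45% for four. This is an upper-end illustration: every covariate sits just under the threshold, and all confound in the same direction.

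**4. Is the method checked?** The complete-case comparison is tied to the imputation analysis. At a site where every covariate is below 15%, there is no imputation analysis, so no comparison is triggered.

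**The case against.** The strongest reply is that the effect is small at the scale of these studies. A moderate confounder (ORs 3 and 1.5) at 14% missing moves VE by less than 1 point, against 14 to 19 points to the lower limit at 500 cases. The larger shifts need strong confounding: ORs 5 and 3 imply a crude VE near 22% when the truth is 50%. That stands, and it limits the weight of the point for a single covariate at a single site.

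The protocol is also generic, with details left to SAPs that are updated annually. That lowers the urgency, but the 15% rule is written as a commitment.

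Some stronger readings are tempting, and the documents do not support them:

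- A reader might infer that every site's adjusted VE is biased. The bias arises only where a confounder is incomplete. Age and sex are obligatory in Annex 1 and have no missing code.
- A reader might infer that VE will always be understated, or that the bias can never cancel. The protocol describes both negative and positive confounding, so opposite signs may partly offset each other, and nothing shows that all sites share one sign.
- A reader might infer that the complete-case analysis could never expose the problem. Where any covariate reaches 15%, that analysis drops records with missing covariate values, which can include those below 15%.
- A reader might infer that counts such as hospitalisations must be turned into categories. The text does not say how numeric covariates are handled, and an indicator plus a constant would keep them numeric.

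Complete case is not a safe replacement either. In a separate set of assumptions (30% prevalence, 30% positivity, 14.9% missing, ORs 3 and 1.5 or 5 and 2, and the same with the influenza OR inverted), missingness depended jointly on vaccination and test result. The indicator method then gave 43.2% to 53.5%, and complete case 28.5% to 66.5%.

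**Conclusion.** The point holds in a limited form. Wherever a confounder is incomplete but under 15% missing, the planned category leaves residual confounding in the adjusted VE, even under MCAR. Under the stated assumptions and a true VE of 50%, one covariate at 14% missing shifts VE by about 1 point for a moderate confounder and by up to about 6 points for a very strong one; the direction follows the sign of the confounding. The actual size cannot be known from the documents.

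For one covariate at a single site of 500 cases, sampling error dominates. The case for changing the rule rests on three things: the bias can accumulate over several incomplete confounders of the same sign, pooling narrows the interval without removing a bias that sites share, and sites with every covariate under 15% have no check on the method. This is a worthwhile improvement, not a defect that invalidates the estimates.

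**What to change.** In the protocol's Missing data section:

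- Apply the multiple imputation already specified to every incomplete confounder, whatever the percentage missing, and state that test result and vaccination status are in the imputation model.
- Delete the missingness-category rule below 15%, or keep it only as a sensitivity analysis.
- Run the complete-case comparison at any level of missingness. Read a difference as a prompt to look at the missingness pattern, since complete case can itself be the more biased of the two.

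The cost is some SAP wording and extra computing at sites. No new data are needed. The analysis would rely on the MAR assumption for more covariates, but the plan already makes that assumption at 15% and above.
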